11 STATISTICAL CONSIDERATIONS

11.1 Study Hypotheses

The primary objective of the study is to clinically validate a *gyrA* assay used to determine ciprofloxacin susceptibility in the treatment of uncomplicated gonococcal infection by assessing the efficacy of ciprofloxacin for treatment of uncomplicated *N. gonorrhoeae* infections with serine 91 *gyrA* genotype as identified by the *gyrA* assay.

The study is designed to test the following hypothesis in the primary efficacy analysis conducted in the per-protocol (PP) analysis population:

Null hypothesis: The proportion of ciprofloxacin-susceptible (as identified by the *gyrA* assay) *N. gonorrhoeae*-infected subjects with microbiological cure 5-10 days after receiving ciprofloxacin is less than 0.95.

Alternative hypothesis: The proportion of ciprofloxacin-susceptible (as identified by the *gyrA* assay) *N. gonorrhoeae*-infected subjects with microbiological cure 5-10 days after receiving ciprofloxacin is at least 0.95.

The cut-off of 0.95 was chosen based on the CDC criteria for treatments of uncomplicated *N. gonorrhoeae* infections. The criterion for recommended treatments is a cure rate of greater than 95% with a lower bound of the 95% confidence interval of at least 95%. The criterion for alternative treatments is a cure rate of greater than 95% with a lower bound of the 95% confidence interval of at least 90%.

[figure not shown]
11.2 Sample Size Considerations

The primary analysis will compute the proportion of ciprofloxacin-susceptible *N. gonorrhoeae*-infected subjects with microbiological cure 5-10 days after receiving ciprofloxacin in the PP analysis population. The confidence interval for the microbiological cure proportion will be computed using a one-sided modified Jeffreys interval using a significance level of 0.05. Power calculations were performed via a simulation study based on 10,000 replications assuming a 98% microbiological cure rate.

Figure 11.2 below presents the power available to test that the microbiological cure rate is at least 95% (i.e., lower bound of the one-sided confidence interval is at least 95%) across a range of evaluable sample sizes. Here, evaluable denotes eligible for the PP analysis population. The power reaches 80% at a sample size of 195 evaluable subjects; however, since the power curve is not monotonic, sample sizes directly on either side of 195 are below 80%. Since the exact number of evaluable subjects at the end of the study is difficult to predict, an evaluable target of 257 subjects is chosen to ensure at least 80% even if the exact number of evaluable subjects at the end of the study differs

slightly from 257. With a target of 257, the power available is approximately 85% and we can fall at most 10 subjects short (sample size of 247 evaluable subjects) and still ensure 80% power. Any sample size greater than 257 will ensure at least 80% power.

Figure 11.2: Power Available to Test That the Microbiological Cure Rate Is at Least 95%

To calculate the number of subjects required to enroll to reach 257 subjects in the PP analysis population, the following assumptions are made:

- 25% of enrolled subjects will be culture negative at baseline.
- 10% of subjects will be excluded from the PP analysis population (reasons for exclusion are stated in section 11.4.1)

Under these assumptions, enrolling 381 subjects will provide 257 subjects in the PP analysis population. Since the proportion of subjects who will be culture negative at baseline can vary depending on a number of factors, 25% is a rough estimate. The exact number of subjects needed to provide 257 subjects in the PP analysis population may vary from 381, so 381 is an approximate enrollment target.

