5. SAMPLE SIZE CONSIDERATIONS

The primary analysis will compute the proportion of ciprofloxacin-susceptible *N. gonorrhoeae*-infected subjects with microbiological cure 5-10 days after receiving ciprofloxacin in the per-protocol analysis population. The confidence interval for the microbiological cure proportion will be computed using a one-sided modified Jeffreys interval using a significance level of 0.05. Power calculations were performed via a simulation study based on 10,000 replications assuming a 98% microbiological cure rate.

Figure 1 presents the power available to test that the microbiological cure rate is at least 95% (i.e., lower bound of the one-sided confidence interval is at least 95%) across a range of evaluable sample sizes. Here, evaluable denotes eligible for the PP analysis population. The power reaches 80% at a sample size of 195 evaluable subjects; however, since the power curve is not monotonic, sample sizes directly on either side of 195 are below 80%. Since the exact number of evaluable subjects at the end of the study is difficult to predict, an evaluable target of 257 subjects is chosen to ensure at least 80% even if the exact number of evaluable subjects at the end of the study differs slightly from 257. With a target of 257, the power available is approximately 85% and we can fall at most 10 subjects short (sample size of 247 evaluable subjects) and still ensure 80% power. Any sample size greater than 257 will ensure at least 80% power.

To calculate the number of subjects required to enroll to reach 257 subjects in the PP analysis population, the following assumptions are made:

- 25% of enrolled subjects will be culture negative at baseline.
- 10% of subjects will be excluded from the PP analysis population (reasons for exclusion are stated in Section 6.3)

Under these assumptions, enrolling 381 subjects will provide 257 subjects in the PP analysis population. Since the proportion of subjects who will be culture negative at baseline can vary depending on a number of factors, 25% is a rough estimate. The exact number of subjects needed to provide 257 subjects in the PP analysis population may vary from 381, so 381 is an approximate enrollment target.

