6. GENERAL STATISTICAL CONSIDERATIONS

6.1. General Principles

Tabulations will be used extensively to summarize the data. All continuous variables will be summarized using some or all of the following descriptive statistics: n (samples size), mean, standard deviation, median, maximum, and minimum. The frequency and percentages (based on the sample size) of observed levels will be reported for all categorical measures. Modified Jeffreys confidence intervals (CIs) for binomial proportions will be computed for efficacy variables [2]. A 5% one-sided significance level will be used; i.e. one-sided 95% confidence intervals will be generated. In general, all data will be listed, sorted by site and subject, and when appropriate by visit number within subject. All summary tables will be annotated with the total population size relevant to that table, including any missing observations.

Note that in the data listing, Subject ID is the unique subject identifier, not the Study ID used on study, and dates will not be included, only Study Day. Study Day 1 will be the day of the dose of treatment.

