6.1.1. Pseudo Code

The following SAS® pseudo code will be used to calculate the following:

Lower bound of the one-sided 95% Jeffreys CI for proportions/percentages if the number of cures is less than the number of subjects included in the analysis:

```
proc freq;  
    tables cure / alpha=0.1 binomial(jeffreys);  
run;
```

Lower bound of the one-sided 95% Jeffreys CI for proportions/percentages if the number of cures is equal to the number of subjects (n) included in the analysis:

```
CI_Lower = 0.05** (1/n);
```

95% Wilson CI for proportions/percentages:

```
proc freq;  
    Table treatment*analysisvariable / alpha=0.1 binomial(wilson);  
    ods output binomialcls=outputdsn;  
run;
```

95% Exact Blaker CI for proportions/percentages:

```
proc freq;  
    Table treatment*analysisvariable / alpha=0.1 binomial(blaker);  
    ods output binomialcls=outputdsn;  
run;
```

95% Agresti-Coull CI for proportions/percentages:

```
proc freq;  
    Table treatment*analysisvariable / alpha=0.1 binomial(AC);  
    ods output binomialcls=outputdsn;  
run;
```

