8.1.1. Sensitivity Analyses

A sensitivity analysis of the primary outcome will be performed to assess the impact of the choice of confidence interval. The primary analysis will be repeated using three different kinds of confidence intervals for binomial proportions: Wilson, Agresti-Coull, and Blaker intervals [2]. The summary of microbiological cure number, microbiological cure rate, and one-sided 95% confidence intervals by analysis population will be presented. See Table 9.

Additional sensitivity analyses of the primary outcome measure will be performed with modifications to the definition of the micro-ITT and PP populations. First, the micro-ITT and PP populations will be modified such that subjects with culture-positive but unknown (indeterminate or missing) *gyrA* results will be included as well as subjects with wild-type only infections. For each subject, all infected sites (whether the infection is wild-type or unknown) will be considered in determining the subject's cure status. Next, the primary analysis will be repeated in the alternate PP population described in Section 6.3.2.3. See Table 10.

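### The 0.05 level of the primary test is nominal: at the target of 257, and at every accepted shortfall down to 247, the exact one-sided error is above 5% (5.4% to 7.0%), and neither document says so

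*Protocol*

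**What the plan says.** The level appears in three places. Protocol 11.2 states: "The confidence interval for the microbiological cure proportion will be computed using a one-sided modified Jeffreys interval using a significance level of 0.05". SAP section 5 repeats this, and SAP 6.1 adds: "A 5% one-sided significance level will be used". The null hypothesis in protocol 11.1 is that the proportion with "microbiological cure 5-10 days after receiving ciprofloxacin is less than 0.95". Protocol 11.2 describes success as the "lower bound of the one-sided confidence interval is at least 95" per cent.

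On sample size, SAP section 5 (like protocol 11.2) says: "With a target of 257, the power available is approximately 85% and we can fall at most 10 subjects short". It assumes a true cure rate of 98% and treats 247 evaluable subjects as still acceptable. Both documents explain that power is not monotonic in the sample size. Neither gives an attained type I error. Protocol 11.3.1 says the futility review leaves power and type I error as described in section 11.2, but that section contains only the 0.05.

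On sensitivity, SAP 8.1.1 says: "The primary analysis will be repeated using three different kinds of confidence intervals for binomial proportions: Wilson, Agresti-Coull, and Blaker intervals". The code heading in SAP 6.1.1 for the last of these reads "95% Exact Blaker CI for proportions/percentages".

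**The concern.** A reader of protocol 11.2 and SAP 5 will take 5% as the chance that a regimen curing exactly 95% passes the test. The Jeffreys bound does not guarantee that. With a binomial count its true error moves above and below the nominal level as the sample size changes. The plan worked through this sawtooth for power, which is why it chose 257 rather than 195, but shows no matching check for the error.

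The trial is single-arm, and the claim is made against a fixed benchmark that protocol 11.1 ties to the criterion for a recommended treatment. One failure more or less can decide the result. If the attained error is not printed beside the power, the reader sees an 85% power figure without the error rate that goes with it.

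**Working it through.** **Inputs.** Level 0.05, one-sided (protocol 11.2, SAP 6.1). Benchmark 0.95 (protocol 11.1). Assumed cure rate 0.98, target 257, floor 247 (protocol 11.2). The bound follows the SAP 6.1.1 code, "tables cure / alpha=0.1 binomial(jeffreys"), whose lower limit is the 0.05 quantile of Beta(X + 0.5, N − X + 0.5) for X cures in N. Protocol 11.4.3.1 prints the 0.95 quantile instead. The stated power reproduces only with the 0.05 quantile, so that is used here; the printed quantile is a separate matter.

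**Step 1: the cut-off.** For each N, find the largest number of failures f for which the Jeffreys bound is at least 0.95. At N = 257, 7 failures (250 cures) give 0.9519, which passes; 8 failures give 0.9470, which does not. At N = 247, 7 failures (240 cures) give 0.95001, which passes narrowly.

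**Step 2: reproduce the plan's figures.** Power = P(Bin(N, 0.02) ≤ f).
- N = 257, f = 7: 0.854, against the stated approximately 85%.
- N = 195, f = 5: 0.802, against 80%; N = 194 and 196 give 0.653 and 0.799, both below 80% as stated.
- N = 247, f = 7: 0.875; N = 246, f = 6: 0.775. This matches the statement that at most 10 subjects can be lost.

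The plan's rule and power are therefore correctly identified.

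**Step 3: the error of the same rule.** Error = P(Bin(N, 0.05) ≤ f). The last two columns show the largest cut-off whose exact error is at most 5%.

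| N | Jeffreys: failures allowed | Exact error | Power at 98% | Cut-off holding 5% | Its power |
|---|---|---|---|---|---|
| 247 | 7 | 7.02% | 87.5% | 6 | 77.2% |
| 250 | 7 | 6.50% | 86.9% | 6 | 76.4% |
| 257 | 7 | 5.40% | 85.4% | 6 | 74.3% |
| 259 | 7 | 5.12% | 84.9% | 6 | 73.7% |
| 260 | 7 | 4.98% | 84.7% | 7 | 84.7% |
| 272 | 7 | 3.58% | 81.9% | 7 | 81.9% |
| 273 | 8 | 6.85% | 90.0% | 7 | 81.6% |

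Seven failures are allowed at every N from 247 to 259, and the error falls steadily from 7.0% to 5.1% over that range. It includes the target and the whole accepted shortfall. With 6 failures the error is 2.5% at 257 and 3.4% at 247.

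**Step 4: the sensitivity intervals with 7 failures.** Lower bounds, each at one-sided 95% (alpha = 0.1 two-sided):

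| Interval | 250/257 | 240/247 |
|---|---|---|
| Jeffreys | 95.19% | 95.00% |
| Wilson | 95.05% | 94.85% |
| Blaker | 95.03% | 94.83% |
| Agresti-Coull | 94.98% | 94.78% |
| Clopper-Pearson (not planned) | 94.95% | 94.74% |

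At 247 all three planned alternatives fail. At 257 Wilson and Blaker pass and Agresti-Coull fails. Blaker's interval is exact as a two-sided interval. Its 90% lower limit is not an exact one-sided 95% bound, which is why it passes at 250/257 although the exact tail is 5.4%. Agresti-Coull agrees with Clopper-Pearson at every N from 247 to 257, but passes 7 failures at 258 (95.002%) and 259 (95.02%), where the exact error is still above 5%.

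**The case against.** The strongest reply is that nothing has been miscalculated. The plan names a published approximate interval, gives its nominal level, and every power figure reproduces. Over N = 240 to 300 the exact error of the rule averages 5.01%, ranges from 3.5% to 7.0%, and is above 5% at 28 of 61 sizes. The excess at the target is 0.4 points. It is also a maximum over the null: at a true cure rate of 94.5% the error is 2.6% at 257 and 3.6% at 247, and at 94.9% it is 4.7% at 257. The formal null excludes 95% itself, although the error approaches 5.4% as the rate approaches 95%. All of this stands. It makes the point one of disclosure, but does not remove it, because the planned size and its whole accepted shortfall lie on the liberal side of that average.

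The reply is also right that the sensitivity analyses do real work. A pass at 240/247 would be contradicted by all three alternatives, and one at 250/257 by Agresti-Coull. A reader might infer that the plan would let a borderline pass go unnoticed; Table 9 as planned would show the disagreement.

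A reader might also infer that 260 must replace 257, or that success should require an exact bound. The documents do not support either. The final per-protocol count cannot be fixed in advance: 259 gives 5.12%, 260 gives 4.98%, and the error rises again to 6.85% at 273. An exact requirement would replace the pre-specified primary rule and cut power to about 74% at 257 to 259 and to between 78.6% and 79.9% at 280 to 285. That is a trade-off for the sponsor, not a correction.

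**Conclusion.** The stated one-sided level of 0.05 is not attained at the planned size. At 257 the exact error is 5.4%, at 247 it is 7.0%, and it exceeds 5% at every size between them and on to 259. The 85% power at 257 belongs to the 5.4% test; a cut-off holding 5% there has 74.3% power, below the plan's own 80%.

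This rests on independent binomial outcomes, the SAP's 0.05 quantile, and evaluation at the 95% boundary. A reader might take the drop to 74.3% to mean that the trial is badly undersized. It does not show that: three more evaluable subjects give 84.7% power with an error of 4.98%, so the dependence is local to sizes around 257. The defect is that the documents present a nominal level as the level of the test and refer, in protocol 11.3.1, to a type I error that section 11.2 never quantifies.

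**What to change.** 1. In protocol 11.2 and SAP 5, call 0.05 the nominal level and print the attained exact error at a 95% cure rate beside the power: 7.0% and 87.5% at 247; 5.4% and 85.4% at 257; 4.98% and 84.7% at 260. Mark 0.05 as nominal in SAP 6.1 too.
2. In protocol 11.3.1, make the reference to type I error point to those values.
3. Add the one-sided 95% Clopper-Pearson bound to SAP 6.1.1, 8.1.1 and Table 9 as a further sensitivity interval. Keep Wilson, Agresti-Coull and Blaker, and note that the alpha = 0.1 Blaker lower limit is not an exact one-sided 95% bound.

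Jeffreys remains the primary rule and 257 the target. The cost is a few sentences, one more code block and one more row per population in Table 9. The downside is that the stated error looks slightly less favourable than 5%.

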11.3 Planned Analyses

11.3.1 Planned Futility Review

The study will be monitored for futility. The number of treatment failures among subjects eligible for the PP analysis population will be monitored by a statistician independent from the study team. If, at any point in the trial, 30 subjects eligible for the PP analysis population are classified as treatment failures, then the statistician will notify DMID to consider termination of the trial.

The cut-off was chosen because 29 or fewer treatment failures among 257 subjects eligible for the PP analysis population would result in a lower bound of the one-sided 95% Jeffreys confidence interval greater than or equal to 85%. Under the protocol's assumptions of the cure rate, a simulation study based on 50,000 replications found that the operating characteristics (power and type-I error) of this futility review do not vary from those described in section 11.2.

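### The 0.05 level of the primary test is nominal: its exact type I error is 5.4% at the target of 257 evaluable subjects and 5.4% to 7.0% across the accepted shortfall range 247–257

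*Protocol*

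**What the plan says.** The null hypothesis in Protocol 11.1 is that the proportion with "microbiological cure 5-10 days after receiving ciprofloxacin is less than 0.95". Protocol 11.2 sets the test: "The confidence interval for the microbiological cure proportion will be computed using a one-sided modified Jeffreys interval using a significance level of 0.05". Success means that the "lower bound of the one-sided confidence interval is at least 95" per cent. SAP 6.1 repeats the level: "A 5% one-sided significance level will be used; i.e. one-sided 95% confidence intervals will be generated". SAP 8.1 calls the comparison with 0.95 a formal hypothesis test, and SAP 6.1.1 implements the bound with "tables cure / alpha=0.1 binomial(jeffreys").

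On sample size, Protocol 11.2 says "Power calculations were performed via a simulation study based on 10,000 replications assuming a 98% microbiological cure rate". It notes that the power curve is not monotonic, chooses 257 evaluable subjects for that reason, and adds that "we can fall at most 10 subjects short (sample size of 247 evaluable subjects) and still ensure 80% power". SAP 5 repeats this. Any size above 257 is also described as adequate.

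Protocol 11.3.1 reports that a simulation "found that the operating characteristics (power and type-I error) of this futility review do not vary from those described in section 11.2". Section 11.2 gives no type I error figure other than the 0.05 itself.

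**The concern.** The modified Jeffreys interval is approximate. With a binomial outcome, the chance that its lower bound clears 0.95 when the true rate is 0.95 moves up and down with sample size, as power does. The plan uses that non-monotonicity to justify 257 and the floor of 247, but shows only the power side.

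The floor of 247 is the size at which a seventh failure becomes allowable. From 246 to 247, power rises from 77.5% to 87.5% and type I error doubles from 3.5% to 7.0%. The whole cushion therefore lies where the test runs above 5%.

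The trial has one formal decision, whether the cure rate meets 95%. A reader who takes 0.05 as the false-positive rate at 257, or at any size in the cushion, is misled, mildly at the target and more clearly at 247.

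**Working it through.** **Inputs.** Null boundary 0.95 (Protocol 11.1). One-sided level 0.05 (Protocol 11.2, SAP 6.1). Assumed cure rate 0.98, target 257, floor 247 (Protocol 11.2). Bound from the SAP 6.1.1 code: the lower limit of a two-sided 90% Jeffreys interval, which is the 0.05 quantile of Beta(X + 0.5, N − X + 0.5) for X cures in N subjects, or 0.05^(1/N) when X = N.

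Protocol 11.4.3.1 prints the 0.95 quantile instead. Read literally that is an upper bound, with type I error of about 94% at N = 257. The 0.05 quantile is used here because it matches the SAP code and reproduces the plan's power.

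**Step 1: the rule.** For each N, find the largest failure count f whose lower bound is at least 0.95. At N = 257, f = 7 gives 0.95194 (pass) and f = 8 gives 0.94698 (fail). At N = 247, f = 7 gives 0.95001 (pass). The limit is f = 7 for all N from 247 to 272, and 8 for 273 to 298.

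**Step 2: reproduce the plan's power.** Power = P(failures ≤ f), with failures ~ Binomial(N, 0.02).

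- N = 195: 80.2%, with 65.3% at 194 and 79.9% at 196. The plan says 80% is reached at 195 and not on either side.
- N = 257: 85.4%. The plan says approximately 85%.
- N = 247: 87.5%, against 77.5% at 246. The plan gives 247 as the floor.
- Minimum from 257 up to the largest N checked (449): 81.9%, at 272. The plan says at least 80%.

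All agree, so this is the rule the plan used.

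**Step 3: exact type I error with the same rule.** Type I error = P(failures ≤ f), with failures ~ Binomial(N, 0.05). This is the error at the boundary, its largest value under the null.

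| N | Failures allowed | Exact type I error | Power at 98% |
|---|---|---|---|
| 246 | 6 | 3.53% | 77.5% |
| 247 | 7 | 7.02% | 87.5% |
| 250 | 7 | 6.50% | 86.9% |
| 253 | 7 | 6.00% | 86.2% |
| 257 | 7 | 5.40% | 85.4% |
| 259 | 7 | 5.12% | 84.9% |
| 260 | 7 | 4.98% | 84.7% |
| 272 | 7 | 3.58% | 81.9% |
| 273 | 8 | 6.85% | 90.0% |
| 285 | 8 | 5.06% | 87.9% |
| 286 | 8 | 4.93% | 87.7% |

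Every N from 247 to 259 is above 5%, as is every N from 273 to 285. Every N from 260 to 272 is below it.

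**Step 4: average over a random N.** The plan's attrition assumptions give an evaluable fraction of 0.75 × 0.90 = 0.675, and 381 × 0.675 = 257.2. Treating N as Binomial(381, 0.675), which is an assumption of this check, the average type I error is 5.2%. About 53% of realised N have an error above 5%.

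**Step 5: the critical count.** The exact one-sided p-value is P(failures ≤ 7 | N, 0.05). The other columns are lower bounds at 7 failures.

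| N | Jeffreys | Wilson | Agresti-Coull | Blaker | Exact p |
|---|---|---|---|---|---|
| 247 | 0.95001 | 0.9485 | 0.9478 | 0.9483 | 0.070 |
| 257 | 0.9519 | 0.9505 | 0.9498 | 0.9503 | 0.054 |

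At 247 Jeffreys passes and all three planned sensitivity intervals fail. At 257 only Agresti-Coull fails. An exact binomial test at 0.05 would allow 6 failures at 257, with type I error 2.55% and power 74.3%.

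**The case against.** The strongest reply is that no printed figure is wrong. SAP 6.1 explains the 5% level as the generation of one-sided 95% intervals, which describes a nominal level, and neither document promises strict control. Jeffreys is an accepted interval. Over N from 150 to 450 its error averages 5.06% and exceeds 5% at 49% of sizes. Preferring near-nominal average behaviour to guaranteed size is a legitimate choice. This stands, and it is why the point is about reporting and not about replacing the method.

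A second reply is that 247–257 is an unfavourable window. The plan also accepts every larger N, and 7.0% applies only at 247 with a true rate of exactly 95%. At a true rate of 94%, the chance of success is 1.2% (N = 257) to 1.7% (N = 247). This also stands. But 257 is the target and 247 is the plan's own floor, so these are the sizes for which a reader needs the figure.

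A third reply is that SAP 8.1.1 and Table 9 already repeat the analysis with Wilson, Agresti-Coull and Blaker intervals. That would expose the fragility at 247. It helps only in part, because at 257 two of the three agree with Jeffreys, and nothing tells the reader what error rate the primary rule carries.

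Three stronger readings are tempting, and the documents do not support them:

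- **That type I error was never examined.** Protocol 11.3.1 mentions it among the simulated operating characteristics. Only the absence of a reported figure can be shown.
- **That the futility review disturbs the error rate.** Flagging the trial at 30 failures cannot create a success when only 7 or 8 failures are allowed. Nor do the documents establish at which cure rate type I error was simulated. The section refers only to the assumed cure rate, and 11.2 names 98%, at which the null is false.
- **That aiming for 260–272 would make both stated figures true.** On the same binomial model, enrolling 386 puts N in that band only 45% of the time. The chance of an error above 5% falls only from 53% to 48%.

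**Conclusion.** The point holds as one of reporting. The stated 0.05 is the nominal level of the interval. The exact type I error is 5.4% at the target and 5.4% to 7.0% over 247–257, with about 5.2% as the average over a random N. The excess at the target is 0.4 percentage points. It matters mainly because the critical count is on the line: 7 failures in 257 is a success under Jeffreys with an exact p-value of 0.054.

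The fixed-N results rest on independent binomial outcomes, the 0.05 quantile as coded in the SAP, and a true cure rate at the 95% boundary. The averages also rest on the plan's 25% and 10% attrition figures. The power figures in Protocol 11.2 are correct, and the result does not call for another primary method or sample size.

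**What to change.** 1. In Protocol 11.2 and SAP 5 and 6.1, describe 0.05 as the nominal one-sided level. Give the exact type I error at a 95% cure rate beside the power: 5.4% at N = 257 and 5.4% to 7.0% for N = 247–257.
2. In SAP 8.1 and Table 8, keep the modified Jeffreys bound as the decision rule and print beside it the exact one-sided binomial p-value, P(failures ≤ observed | N, 0.05). Add a note that the Wilson, Agresti-Coull and Blaker intervals in Table 9 can disagree with the primary rule at the critical count, for example at 7 failures in 247.
3. In Protocol 11.3.1, state which cure rate was used to evaluate type I error.

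The cost is a few sentences and one line in Table 8. The enrolment target and the primary rule do not change. The only downside is that the stated error rate becomes slightly less favourable.
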